#### Summary

Dual antiplatelet therapy (DAPT) with aspirin and a  $P2Y_{12}$  receptor inhibitor, more frequently clopidogrel, represents the standard of care for the long-term secondary prevention of atherothrombotic events in patients with myocardial infarction (MI) or peripheral arterial disease (PAD). However, rates of ischemic recurrences remain high, in part due to the fact that other platelet signaling pathways, such as thrombin-induced platelet aggregation, continue to be activated. Vorapaxar is a novel, orally active, competitive and slowly reversible protease-activated receptor (PAR)-1 inhibitor, which exerts potent inhibition of thrombin-mediated platelet aggregation. It is approved for clinical use by the Food and Drug Administration for the reduction of thrombotic cardiovascular events in patients with a history of MI or with PAD. Patients with DM are known to be at increased risk of recurrent atherothrombotic events, which translates into worse outcomes, despite the use of standard of care therapy. This is in part due to the hyperreactive platelet phenotype, which characterizes DM patients, and to inadequate response to oral antiplatelet agents, including clopidogrel. Importantly, in DM patients with prior MI included in the TRA 2P trial, vorapaxar reduced the primary composite end point at 3 years by 27% and led to a greater absolute risk reduction compared with those without DM. Therefore, vorapaxar is an attractive treatment option for DM patients with a prior MI. However, to date the PD effects of vorapaxar in DM patients and how these may differentiate from non-DM patients has not been explored. Further, current trends in clinical practice are seeing many patients discontinue aspirin and maintain clopidogrel. Hence, the role of vorapaxar as part of a dual antithrombotic treatment regimen combined with clopidogrel (and stopping aspirin) represents another important area of clinical

interest, in order to maximize ischemic protection while reducing the risk of bleeding. The proposed prospective, parallel-design study conducted in post-MI and PAD patients with and without DM will aim the assess the pharmacodynamic effects of vorapaxar in addition to standard DAPT with aspirin and clopidogrel as well as in combination with clopidogrel only following aspirin withdrawal. Pharmacodynamic assessments will be performed at multiple time point, with different assays exploring multiple pathways of platelet aggregation.

# **Background and Significance**

Dual antiplatelet therapy (DAPT) with aspirin and a  $P2Y_{12}$  receptor inhibitor represents the standard of care for the long-term secondary prevention of atherothrombotic events in patients with myocardial infarction (MI) [1]. Clopidogrel is the most widely used P2Y12 receptor inhibitor and the use of DAPT with aspirin and clopidogrel has consistently demonstrated to reduce the risk of thrombotic recurrences in patients with acute coronary syndrome (ACS) [2]. However, despite this treatment regimen, rates of ischemic recurrences remain elevated, especially in high risk patients. such as those with diabetes mellitus (DM) [2-4]. This is in part due to the fact that other platelet signaling pathways, such as thrombin-induced platelet aggregation, continue to be activated and can thus contribute to thrombus formation [5,6]. In particular, thrombin is one of the most potent platelet activators, and the surface of activated platelets is the main source of circulating thrombin [5-7]. Vorapaxar is a novel, orally active, highly selective, competitive and slowly reversible protease-activated receptor (PAR)-1 inhibitor, which exerts potent inhibition of thrombin-mediated platelet aggregation [8,9]. Pharmacokinetic studies have shown that vorapaxar has a dissociation half-life as long as 20 hours which leads to consistent pharmacodynamic (PD) effects [8,9]. Importantly, when vorapaxar is added to DAPT, enhanced P2Y12 inhibition has been shown due to the potential interplay between purinergic and thrombin-mediated platelet signaling pathways [10]. Recently, vorapaxar (2.5 mg once daily) has been approved for clinical use by the US Food and Drug Administration (FDA) and by the European Medicines Agency for the reduction of thrombotic cardiovascular events in patients with a history of MI or with peripheral arterial disease (PAD), and should be used in addition to standard-of-care antiplatelet therapy with aspirin and/or clopidogrel [11,12]. These indications are largely attributed to the findings of the TRA 2P-TIMI 50 (Thrombin Receptor Antagonist in Secondary Prevention of Atherothrombotic Ischemic Events - Thrombolysis

in Myocardial Infarction 50) trial [13]. In particular, the trial showed that the use of vorapaxar in addition to standard antiplatelet therapy was effective in the secondary prevention of recurrent thrombotic events (cardiovascular death, MI, or stroke) in patients with previous atherothrombosis, particularly those with prior MI and PAD, albeit at the cost of increased bleeding [13,14].

Patients with DM are known to be at increased risk of recurrent atherothrombotic events, which translates into worse outcomes, despite the use of standard of care therapy [4,15]. This is in part due to the hyperreactive platelet phenotype with upregulation of multiple platelet signaling pathways, including thrombin, which characterizes patients with DM [4]. Importantly, increased platelet reactivity may account for inadequate response (i.e. reduced platelet inhibitory effects) to oral antiplatelet agents, including the  $P2Y_{12}$  receptor antagonist clopidogrel, contributing to worse outcomes [4]. Notably, in DM patients and prior MI included in the TRA 2P trial, vorapaxar reduced the primary composite end point at 3 years by 27% (p=0.002), and led to a greater absolute risk reduction (absolute risk difference: -3.50%) compared with those without DM (absolute risk difference: -1.36%) with a number needed to treat of 29 [16]. The benefit of vorapaxar was also consistent in patients with PAD, although no specific subgroup data are available based on DM status [17]. Therefore, patients with DM, characterized by diffuse atherothrombotic disease manifestations and enhanced risk of ischemic recurrences, seem particularly attractive for treatment with vorapaxar. However, to date the PD effects of vorapaxar in patients with DM, as well as the comparative effects of DM versus non-DM patients has not yet been explored.

## **Study Rationale and aims**

Despite the encouraging clinical findings from TRA-2P and the potential for an uptake of vorapaxar in daily practice, there is limited data on the PD effects of vorapaxar as an add-on therapy in key high-risk settings, such as prior MI or PAD patients with DM, where enhanced platelet

inhibition by means of PAR-1 blockade, may be more clinically beneficial. Further, given the length of the TRA-2P trial (median follow-up of 30 months), many patients were enrolled in the trial while on standard DAPT with aspirin and clopidogrel, but then interrupted one antiplatelet agent as per standard of care [13]. Although most patients discontinue clopidogrel therapy and continue aspirin, current trends in clinical practice are seeing many patients discontinue aspirin and maintain clopidogrel, which provides more comprehensive platelet inhibition compared with aspirin [18]. Hence, the role of vorapaxar as part of a dual antithrombotic treatment regimen combined with clopidogrel (and stopping aspirin) represents another important area of clinical interest, in order to maximize ischemic protection while reducing the risk of bleeding. Further, the comparative PD effects of vorapaxar in addition to different combination of antiplatelet therapy in patients with DM versus those without DM is currently unknown. A comprehensive understanding of the PD effects of vorapaxar as an add-on therapy will thus be informative to the practicing clinician. Therefore, the aim of the proposed investigation is to assess the PD effects of vorapaxar in addition to DAPT with aspirin and clopidogrel as well as to antiplatelet therapy with clopidogrel, in the setting of post-MI or PAD patients with and without DM.

### **Research Plan**

### Study Population

#### *Inclusion criteria*:

- 1. Patients with a prior MI between 2 weeks and 24 months or with PAD.
- On DAPT with low-dose aspirin (81mg od) and clopidogrel (75mg od) as per standard-of-care for at least 14 days.
- 3. Age  $\geq$  18 years old.

4. Patients entering the DM cohort will need to have diagnosis of type 2 DM defined according to the WHO definition [19], on treatment with oral hypoglycemic agents and/or insulin for at least two months, without any changes in regimen.

#### *Exclusion criteria*:

- 1. History of ACS in the previous 2 weeks.
- 2. History of stroke, transient ischemic attack, or intracranial hemorrhage.
- 3. Active pathological bleeding, history of bleeding events or increased risk of bleeding.
- 4. Known severe hepatic impairment.
- 5. Type 2 DM on dietary control.
- 6. Use of strong CYP3A inhibitors (e.g., ketoconazole, itraconazole, posaconazole, clarithromycin, nefazodone, ritonavir, saquinavir, nelfinavir, indinavir, boceprevir, telaprevir, telithromycin and conivaptan) or inducers (e.g., rifampin, carbamazepine, St. John's Wort and phenytoin).
- 7. On treatment with any oral anticoagulant (vitamin K antagonists, dabigatran, rivaroxaban, apixaban, edoxaban).
- 8. On treatment with any antiplatelet agent other than aspirin and clopidogrel in the past 14 days.
- 9. Creatinine clearance <30 mL/minute.
- 10. Platelet count  $< 80 \times 10^6$ /mL
- 11. Hemoglobin <10g/dL
- 12. Hemodynamic instability
- 13. Pregnant females [women of childbearing age must use reliable birth control (i.e. oral contraceptives) while participating in the study].

#### Laboratory assessments

Peripheral venous blood samples (20 mL) will be drawn through a short venous catheter inserted into a forearm vein and collected in citrate, EDTA, and serum tubes as appropriate for assessments. The first 2-4 mL of blood will be discarded to avoid spontaneous platelet activation. Blood sampling for PD will be performed at 3 time points as indicated above in the study design section. Various PD assays will be performed as described below. Given the potential interplay between PAR-1 and P2Y12 mediated signaling, assessments specific for both pathways will be conducted [10]:

- 1. Light transmittance aggregometry (LTA)
- 2. Whole blood vasodilator-stimulated phosphoprotein (VASP)
- 3. VerifyNow P2Y12
- 4. Thrombelastograph Coagulation Analyzer TEG 6s Series system (CORA® system)
- 5. Serum thromboxane B2

## Description of laboratory assays

1) Light transmittance aggregometry (LTA): Platelet aggregation will be performed using LTA according to standard protocols. Blood will be collected in citrated (3.8%) tubes. LTA will be assessed using platelet rich plasma (PRP) by the turbidimetric method in a 2-channel aggregometer (Chrono-Log 490 Model, Chrono-Log Corp., Havertown) as previously described [23,24]. Platelet agonists will include AA (1 mM), collagen ( $3\mu g$ /ml), ADP (5 and 20  $\mu$ M), TRAP (15  $\mu$ M), and a combination of 2  $\mu$ g/ml collagen-related peptide + 5  $\mu$ M ADP + 15  $\mu$ M TRAP (CAT). The reagent cocktail CAT will allow to assess the overall platelet response to a combination of agonists that leads to activation of multiple platelet pathways. PRP will be obtained as a supernatant after centrifugation of citrated blood at 1000 rpm for 10 minutes. The isolated PRP will be kept at 37° C before use. Platelet poor plasma (PPP) will be obtained by a second centrifugation of the blood fraction at 2800 rpm for 10 minutes. Light transmission will be adjusted to 0% with the PRP and to 100% for the PPP for each measurement. Curves will be recorded for 6 minutes and platelet aggregation will be determined as the maximal percent change (MPA) in light transmittance from baseline using PPP as a reference.

2) Whole blood vasodilator-stimulated phosphoprotein (VASP): VASP phosphorylation (VASP-P) is a marker of P2Y12 receptor reactivity. VASP will be assessed according to standard protocol using labeled monoclonal antibodies by flow cytometry with the Platelet VASP-FCM kit (Biocytex Inc., Marseille, France) as previously described [25]. PGE1 increases VASP-P levels by stimulation of adenylate cyclase. Binding of ADP to P2Y12 leads to Gi-coupled inhibition of adenylate cyclase. Therefore, the addition of ADP to PGE1-stimulated platelets reduces PGE1-induced VASP-P levels. If P2Y12 receptors are successfully inhibited by inhibitors, addition of ADP will not reduce the PGE1-stimulated VASP-P levels. The platelet reactivity ratio (PRI) will be calculated after measuring VASP-P levels after stimulation with PGE1 (MFI PGE1) and also PGE1 + ADP (MFI PGE1 + ADP). The P2Y12 reactivity ratio = ([MFI PGE1] – [MFI PGE1 + ADP]/[MFI PGE1]) x 100%.

3) VerifyNow (VN) P2Y12: The VerifyNow System is a turbidimetric based optical detection system which measures platelet induced aggregation as an increase in light transmittance (Accumetrics, San Diego, CA) and will be utilized according to manufacturer's instructions, as previously described [25]. The assay is based on microbead agglutination and uses specific reagents for the pathways of interest. The VN-P2Y12 assay, by combining ADP+PGE1, measures changes in platelet function specific to P2Y12 receptor inhibitors. The assay is based upon the ability of activated platelets to bind fibrinogen. Fibrinogen-coated microparticles aggregate in proportion to the number of GP IIb/IIIa receptors expressed. Microbead aggregation is more rapid and reproducible if platelets are activated; therefore the reagents are incorporated into the assay channel to induce platelet activation without fibrin formation. Light transmittance increases as activated platelets bind and aggregate fibrinogen-coated beads. The instrument measures this change in optical signal and reports results in P2Y12 Reaction Units (PRU). 4) TEG 6s Series system (CORA® system): the TEG 6s system (Haemonetics Corporation,

Braintree, MA, USA) will be used according to manufacture instructions [26]. In brief, the CORA® system is a new generation portable thrombelastography technology able to evaluate all phases of hemostasis, including time to clot formation, rate of clot formation, strength of clot and residual clot strength due to antiplatelet drugs, rate of clot lysis. Disposable assay cartridges contain all of the components necessary to allow the analyzer to prepare samples and perform hemostasis tests. The analyzer automatically draws the blood into the active area of the cartridge, meters the exact amount required for the test, and mixes it with the reagents spotted in the cartridge. The analyzer then monitors the harmonic motion of a pendant drop of blood in response to external vibration. As the sample transitions from a liquid state to a gel-like state during clotting, the modulus of elasticity and resonant frequency increase. The instrument measures these variations in resonant frequency during clotting and lysis. The results are displayed in a table and on a graphical tracing that reflects a hemostasis profile of clot formation. The resulting hemostasis profile is a measure of the time it takes for the first measurable clot to be formed, the kinetics of clot formation, the strength of the clot, and the breakdown of the clot, or fibrinolysis. In particular, the PlateletMapping Cartridge are used to assess platelet function in patients who have received platelet inhibiting drugs. The PlateletMapping assay consists of a set of agonists, ADP and arachidonic acid (AA) platelet agonists together with ActivatorF, which can measure the inhibition of platelet function. This assay specifically determines the MA (Maximum Amplitude, a measure of clot strength) and the reduction in MA due to antiplatelet therapy and reports it as a percentage of reduction in clot strength. The assay uses AA and ADP agonists to generate test results that reflect the inhibiting effects of antiplatelet agents such as TxA2 Inhibitors (e.g., aspirin) and ADP P2Y12 inhibitors (e.g., clopidogrel). Since thrombin (present in blood samples) is the primary and most potent activator of

platelets, its activity must be inhibited with heparin so that the platelet activating effects of ADP and AA can be measured. Since thrombin has been rendered inactive by heparin, activatorF is used to replace thrombin's role in the conversion of fibrinogen to fibrin and Factor XIII to Factor XIIIa. Thus, with this cross-linked fibrin network as the foundation, additional clot strength due to platelet-fibrin bonding related to ADP and AA platelet receptor activation can be measured. The HKH reagent, a combination of kaolin and heparinase, generates test data for the uninhibited MA resulting from thrombin activation of the blood sample, while the heparinase neutralizes the effects of heparin. The HKH test provides measures of R (Reaction time; the amount of time between the start of the test and the beginning of coagulation), K (the speed of formation of the clot from R time to a specific clot strength), Angle (the speed of clot strengthening), LY30 (Percent lysis 30 minutes after MA is finalized) and MA parameters; The activatorF test provides the contribution of fibrin to the overall strength of the clot. This test value is used in the calculation of aggregation/inhibition for MA ADP and MA AA. The AA and ADP test provide measures of MA, percent inhibition and percent aggregation.

5) Serum thromboxane B2: The concentration of serum thromboxane B2 (TXB2) will be measured by using the TXB2 EIA kit (Cayman Chemical Company, Ann Arbor, MI) according to the instructions of the manufacturer, as previously described [27]. Briefly, samples will be diluted with EIA buffer to bring their concentrations within the range of the standard curve. No other purification will be performed on any of the samples. A standard curve will be established by serial dilution of TXB2 between 1000 pg/mL and 7.8 pg/mL using EIA buffer as the matrix. The concentration of TXB2 in the samples will be calculated from a logistic 4-parameter fit of the standard concentrations versus percentage bound/maximum bound.

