## Study endpoints and sample size calculation

The primary end point of our study is the comparison of CAT-induced MPA measured by LTA between vorapaxar plus DAPT and vorapaxar plus clopidogrel. We hypothesize that vorapaxar in addition to single antiplatelet therapy with clopidogrel will be non-inferior to vorapaxar in addition to DAPT with aspirin and clopidogrel in MPA after 30±5 days of treatment in both DM and non-DM patients. Under the assumption of 0 difference in mean CAT-induced MPA between vorapaxar plus clopidogrel and vorapaxar plus DAPT and a common standard deviation of 13%, a sample size of 28 patients per group allows for the 95% confidence interval (CI) to stay within  $\pm$ 10% with a 80% power and alpha=0.025. Considering the two groups (DM and non-DM), a total of 56 patients with valid primary end point data will need to be included. Assuming up to 40% rate of invalid results due to haemolysis or drop-out, up to 79 patients will need to be enrolled. Noninferiority will be assessed using a 95% CI of the difference in mean MPA between the 2 arms. As there are no preliminary data in this setting, the 10% non-inferiority margin was arbitrarily defined. Mean values of platelet aggregation and variability were estimated based on previous data of vorapaxar in addition to DAPT with aspirin and clopidogrel [24]. This approach is in agreement with recommendations for pilot investigations [28].

Other objectives will include the comparisons between DM and non-DM patients of all PD parameters measured by multiple assays, and the comparisons between levels of platelet inhibition achieved by DAPT (baseline therapy) versus levels achieved by antiplatelet therapy including vorapaxar. The effects of additive inhibition of the thrombin-mediated platelet activation pathway, with or without aspirin therapy, on serum thromboxane levels will also be evaluated.

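### The VASP reactivity formula is misbracketed: as printed it adds an offset that depends on raw PGE1 fluorescence, so it is not the percentage index the section describes

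*Combined protocol and SAP*

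**What the plan says.** The VASP item under 'Description of laboratory assays' takes two mean fluorescence readings per sample, "after stimulation with PGE1 (MFI PGE1) and also PGE1 + ADP (MFI PGE1 + ADP"), and combines them as "The P2Y12 reactivity ratio = ([MFI PGE1] – [MFI PGE1 + ADP]/[MFI PGE1]) x 100", with a percent sign. No other formula for this parameter appears in the protocol or in the statistical analysis plan section.

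The same item explains how the readings should behave. Without inhibition, "the addition of ADP to PGE1-stimulated platelets reduces PGE1-induced VASP-P levels". At the other extreme, "If P2Y12 receptors are successfully inhibited by inhibitors, addition of ADP will not reduce the PGE1-stimulated VASP-P levels". It also ties the measurement to an established procedure: "VASP will be assessed according to standard protocol using labeled monoclonal antibodies by flow cytometry with the Platelet VASP-FCM kit".

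'Study endpoints and sample size calculation' places VASP among the other objectives, which include "the comparisons between DM and non-DM patients of all PD parameters measured by multiple assays" and comparisons of baseline DAPT with the regimens that contain vorapaxar. The primary end point is a different assay: "The primary end point of our study is the comparison of CAT-induced MPA measured by LTA".

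**The concern.** Nothing in the printed line groups the subtraction. Under ordinary precedence the division applies only to the second term, so a unitless ratio is subtracted from a raw fluorescence value. The result is not a ratio of two readings and is not confined to 0–100%. It also changes when both readings are rescaled together, as they would be with a different cytometer setting.

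At stake is one of the pharmacodynamic parameters to be compared between DM and non-DM patients and across three visits. If the line were coded as it stands, differences in the PGE1 reading would be carried into those comparisons alongside any difference in P2Y12 reactivity.

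**Working it through.** **Inputs.** A = MFI PGE1 and B = MFI PGE1 + ADP, both from the VASP item. The same item implies B ≤ A, since ADP lowers the signal, and B = A under full P2Y12 inhibition. The documents give no MFI values and no worked result, so there is no stated figure to reproduce. All readings below are assumed and are shown over a range.

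**Formulas.**
- As printed: P = (A – B/A) × 100.
- Correctly grouped: R = ((A – B)/A) × 100 = (1 – B/A) × 100.
- Difference: P – R = (A – B/A – 1 + B/A) × 100 = (A – 1) × 100.

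The printed value is therefore the intended index plus an offset that depends only on A. The two agree only when A = 1.

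**Check against the section's own boundary case.** At full inhibition B = A, so R = 0% and P = (A – 1) × 100. This is 900% at A = 10, 9,900% at A = 100 and 99,900% at A = 1000.

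**When P exceeds 100%.** This needs A – B/A > 1, that is A > 1 + B/A. Since B/A is at most 1, it always holds when A > 2.

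**Numerical comparison (assumed readings).**

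| A | B | As printed | Correctly grouped |
|---|---|---|---|
| 1 | 0.5 | (1 – 0.5) × 100 = 50% | 50% |
| 10 | 5 | (10 – 0.5) × 100 = 950% | 50% |
| 20 | 10 | (20 – 0.5) × 100 = 1950% | 50% |
| 40 | 20 | (40 – 0.5) × 100 = 3950% | 50% |
| 100 | 50 | (100 – 0.5) × 100 = 9,950% | 50% |
| 10 | 2 | (10 – 0.2) × 100 = 980% | 80% |

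Doubling both readings from 20/10 to 40/20 moves the printed value by 3950 – 1950 = 2000 points and leaves the correct index unchanged. The order of two samples can also reverse: 10/2 is the more reactive sample (80% against 50% for 20/10), yet its printed value is lower (980% against 1950%).

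**Effect on a comparison.** Taking means of P = R + (A – 1) × 100, the difference between two groups or visits is

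mean difference in P = mean difference in R + 100 × (mean difference in A).

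At a fixed A, going from no inhibition to full inhibition spans 100 points. A mean difference of one fluorescence unit in A contributes those same 100 points. Even where mean A is equal, variation in A between samples enters the variability of P.

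**The case against.** The best defence is that the intent is plain and the assay is anchored elsewhere. The item names a commercial kit and its standard protocol, cites an earlier description, calls the result a ratio and expresses it in percent. Only (A – B)/A fits that account, and laboratory staff would hardly accept 1950% for a percentage index. This stands as a reason to expect the right calculation in practice. It does not make the printed line correct, and that line is the only formula the plan gives. The kit protocol and the citation are not reproduced in the documents. The printed brackets balance, so nothing suggests that one was lost in reading the PDF, although that cannot be fully excluded.

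A reader might also infer that the printed quantity fails to follow P2Y12 inhibition at all, so that every VASP comparison would be meaningless. The algebra does not support that. At a fixed A the printed value falls point for point with the correct index as inhibition rises; the damage comes from differences in A between samples. Nor should the printed result be faulted for not being a percentage of inhibition. The intended index measures reactivity and is 0% at full inhibition.

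Finally, VASP is not the plan's only view of the P2Y12 pathway. VerifyNow P2Y12, LTA with ADP at 5 and 20 µM and the ADP channel of TEG PlateletMapping are also planned.

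**Conclusion.** The point holds as a minor error in operative methods text. The printed VASP formula equals the intended reactivity index plus (A – 1) × 100, exceeds 100% whenever A > 2, and contradicts the section's own description of full inhibition unless A = 1. These are algebraic facts and rest on no outside source. How large the error would be depends on the actual MFI values, which the documents do not give; it would vanish only for a signal scaled to A = 1.

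Distortion of the group and visit comparisons is conditional on the line being applied literally and on A differing between samples. The documents do not show that anyone would apply it literally. A reader might extend the concern to the trial's main result, but CAT-induced MPA by LTA, the 10% margin, the 13% standard deviation and the 28 patients per group make no use of VASP and are unaffected.

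**What to change.** Replace the printed line with PRI = (([MFI PGE1] – [MFI PGE1 + ADP]) / [MFI PGE1]) × 100%, and confirm that whatever calculation produces the analysed VASP values uses this grouping. A quick test is that equal readings return 0% and that 20/10 and 40/20 both return 50%. Using the single label PRI in the item would be a tidy editorial addition. The cost is one line of protocol text and a brief check of the calculation, with no change to design, sampling or sample size.
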